5.5 Treating the patient

5.5.1 Patient numbering

Each subject is uniquely identified in the study by a combination of his/her center number and subject number. The center number is assigned by Novartis to the investigative site. After the subject has signed the ICF, the investigator or his/her staff will contact the IRT and provide the requested identifying information for the subject. At each site, the first subject is assigned subject number 1, and subsequent patients are assigned consecutive numbers (e.g. the second subject is assigned subject number 2; the third subject is assigned subject number 3). Once assigned to a subject, a subject number will not be reused. If the subject fails to be randomized for any reason, the IRT must be notified within 2 days and the reason for not being randomized will be entered on the Screening Phase Disposition Form within the eCRF. The appropriate eCRF(s) pages should also be completed.

Patients can only be re-screened once and will receive a new subject number after they have been re-consented. Patients who are mis-randomized cannot be re-screened.

5.5.2 Dispensing the investigational treatment

Each study site will be supplied by Novartis with investigational treatment (active treatment or placebo) in packaging of identical appearance.

The investigational treatment packaging has a 2-part label. A unique medication number is printed on each part of this label, which corresponds to placebo or active treatment. Investigator staff will identify the investigational treatment packages to dispense to the subject by contacting the IRT and obtaining the medication numbers. Immediately before dispensing the package to the subject, the investigator staff will detach the outer part of the label from the packaging and affix it to the source document (Drug Label Form) for that subject's unique subject number.

5.5.3 Handling of study treatment

5.5.3.1 Handling of Investigational treatment

Investigational treatment must be received by a designated person at the study site, handled and stored safely and properly, and kept in a secured location to which only the investigator and designees have access. Upon receipt, all investigational treatment should be stored according to the instructions specified on the labels. Clinical supplies are to be dispensed only in accordance with the protocol.

Medication labels will be in English and comply with legal requirements in the U.S. They will include storage conditions for the investigational treatment but no information about the patient except for the medication number.

The PFS (150 mg active/placebo) sealed in their outer box must be stored in a locked refrigerator between 2°C and 8°C (36°F and 46°F) and protected from light. They must be

carefully controlled in accordance with regulations governing investigational medicinal products and local regulations.

The investigator must maintain an accurate record of the shipment and dispensing of investigational treatment in a drug accountability log. Monitoring of drug accountability will be performed by monitors during site visits or remotely and at the completion of the trial. Patients will be asked to return all unused investigational treatment and packaging at the end of the study or at the time of discontinuation of investigational treatment.

At the conclusion of the study, and as appropriate during the course of the study, the investigator will return all unused investigational treatment, packaging, drug labels, and a copy of the completed drug accountability log to the Novartis monitor or to the Novartis address provided in the investigator folder at each site.

Destruction of the unused drug should be done according to local requirements and after approval by Novartis clinical team.

5.5.4 Instructions for prescribing and taking study treatment

All study treatment (150 mg secukinumab, or placebo) will be self-administered subcutaneously throughout the study after the study assessments for the visit have been completed. Site staff will administer the injection only to those patients who are not able to self-administer the PFS injection. Detailed instructions on the self-administration of the study treatment will be described in the Instructions For Use (IFU) and provided to each subject.

The first study treatment administration will occur at the randomization visit (BL) **after** inclusion/exclusion criteria have been confirmed, all study scheduled assessments have been performed and the scheduled blood samples have been drawn.

The subject will be instructed by the site staff, utilizing the IFU, on how to self-inject via PFS. Patients will be asked to raise any questions, if they have any, and then to proceed with self-injection. Self-injection will take place under the supervision of a site staff member. At the Week 1 and subsequent visits, patients will be asked to refer to the IFU and to proceed with self-injection of the study drug.

Study treatment will be administered weekly following the BL dose (Weeks 1, 2, 3, & 4) and every 4 weeks thereafter (Week 8 until Week 48)

All dates and times of injections self-administered by the subject during the study must be recorded on the Dosage Administration Record eCRF. Immediately before dispensing the drug package to the subject, the investigator staff will detach the outer part of the label from the packaging and affix it to the source document (Drug Label Form) for that subject's unique subject number.

The investigator should promote compliance by instructing the subject to attend the study visits as scheduled and by stating that compliance is necessary for the subject's safety and the validity of the study. The subject should be instructed to contact the investigator if he/she is unable for any reason to attend a study visit as scheduled or if he/she is unable for any reason to take the study treatment as prescribed.

5.5.4.1 Administration

Secukinumab Solution for Subcutaneous Injection (active or placebo, respectively) will be provided in prefilled syringes (PFS).

- Secukinumab (active) 150 mg/mL solution in a single-use Sensoready® pen or placebo

Single syringes will be packed in individual boxes. The boxes containing the safety prefilled syringes with study treatment solution should be kept at 2 to 8°C (36°F and 46°F) and protected from light. Prior to administration the boxes containing the safety prefilled syringes with study treatment solution should be allowed to come to room temperature unopened for about 20 minutes before administration. Used safety syringe should be disposed immediately after use in a sharps container.

Patients will be instructed at BL by the site staff on how to self-inject either secukinumab or placebo (blinded) via PFS following the IFU. After the BL visit, the injections will be self-administered into the appropriate site of the body (thighs, arms, abdomen), and each injection should be given at a different injection site. Each new injection should be given at least one inch from the previously used site. If subject chooses the abdomen, 2 inches area around navel should be avoided. Investigational drug should not be injected into areas where the skin is tender, bruised, red, or hard, or where subject has scars or stretch marks. Injection sites should be changed to reduce the risk of reaction.

At study visits when pre-dose blood samples have to be drawn, the study medication will be self-injected only after the blood samples have been taken.

5.5.5 Permitted dose adjustments and interruptions of study treatment

Study treatment dose adjustments are not permitted. Study treatment interruption is also not permitted with the following exceptions:

Study treatment interruption is only permitted if, in the opinion of the investigator, a subject is deemed to be placed at a significant safety risk unless dosing is temporarily interrupted. In such cases study treatment should be interrupted only during the time that this risk is present and ongoing. Study treatment can be restarted at the next scheduled visit after resolution of the safety risk.

The effect of secukinumab on live vaccines is unknown; therefore live vaccines should not be administered during participation in the study. In case a live vaccine has been administered due to a medical urgency, study treatment should be interrupted for 12 weeks. Any study treatment interruption must be recorded on the corresponding Dose Administration Record eCRF page and all assessments should be completed as scheduled.

5.5.6 Rescue medication

Rescue medication is defined as any new therapeutic intervention or a significant change to ongoing therapy made because a subject is experiencing either no benefit from participation in the trial or worsening / exacerbation of their disease.

Rescue medication must not be used before completion of Week 16 assessments.

Changes in NSAIDs concomitant therapy is permitted after Week 16 assessments per investigator's clinical judgment. Any use of rescue medication must be recorded on the corresponding Concomitant Medications eCRF.

Please see [Section 5.5.7](#) for additional details.

5.5.7 Concomitant treatment

The investigator should instruct the patient to notify the study site about any new medications he/she takes after the patient was enrolled into the study. All medications, procedures and significant non-drug therapies (including physical therapy and blood transfusions) administered after the patient was enrolled into the study must be recorded.

Guidelines for the use of specific medications are provided below:

Methotrexate (MTX)

Patients taking MTX (up to 25 mg/week) must be on a stable dose for at least 4 weeks before randomization and maintained stable throughout the duration of the study.

Folic acid

Patients on MTX must be taking folic acid supplementation before randomization and during the study to minimize the likelihood of MTX associated toxicity.

Leflunomide wash-out with cholestyramine

In case of leflunomide treatment, a wash-out of 8 weeks has to be performed.

However, another wash-out procedure might be considered. Cholestyramine could be given orally to wash-out the leflunomide at a dose of 8 g t.i.d. Cholestyramine reduced plasma levels of the active leflunomide metabolite by approximately 40 % in 24 hours and by 49% to 65% in 48 hours in three healthy volunteers. The administration of cholestyramine is recommended in patients who require a drug elimination procedure. If a subject receives 8 g t.i.d. for 11 days, the subject could be safely randomized 4 weeks after the beginning of the 11-day treatment period.

Systemic corticosteroids

Treatment with systemic corticosteroids is permitted up to a maximum daily dosage of 10 mg prednisone equivalent and the dose is stable within the 2 weeks preceding randomization. The subject should remain on a stable dose until Week 16.

Corticosteroid dose reductions below 10 mg prednisone equivalent are permitted after Week 16, although the corticosteroid dose should not be reduced more than 1 mg prednisone equivalent every 4 weeks. Any change in the dose of systemic corticosteroids during the trial must be recorded on the corresponding eCRF page.

Intra-articular corticosteroids are not permitted within the 4 weeks preceding randomization and up to Week 16. After Week 16, no more than one joint per 24-week period may be injected. No single injection should exceed 40 mg of triamcinolone (or equivalent) and the

total dose of intra-articular corticosteroid may not exceed 80 mg of triamcinolone (or equivalent) during the study.

Non-steroidal anti-inflammatory drugs (NSAIDs) (including COX-1 or COX-2 inhibitors), low strength opioids and acetaminophen

Patients on regular use of NSAIDs, low strength opioids, or acetaminophen PRN should be on stable dose for at least 2 weeks before randomization to allow inclusion. They should remain on a stable dose during the study up to Week 16; however, they have to refrain from any intake at least 1 day before a visit with disease activity assessments.

After the Week 16 assessments are completed, a change in the NSAIDs, low strength opioids, or acetaminophen treatment regimen is permitted

Any change of the NSAIDs, low strength opioids, or acetaminophen treatment during the trial should be recorded on the corresponding eCRF page.

5.5.8 Prohibited treatment

Patients who received any biologics such as etanercept, infliximab, adalimumab, golimumab, certolizumab, ustekinumab, cocilizumab, abatacept or rituximab before this study are not allowed to participate in this trial.

Use of the treatments displayed in [Table 5-1](#) below is **NOT** allowed during the study for any indication unless otherwise specified; wash-out periods for these treatments are provided in [Table 5-1](#). If the use of any of these treatments is required, then the subject must not be randomized into the study.

Table 5-1 Prohibited medication

Prohibited treatments	Washout period (before randomization)
Conventional DMARDs (except MTX) including [REDACTED]	4 weeks
Leflunomide	8 weeks
Leflunomide with cholestyramine washout	4 weeks
Any investigational treatment or participation in any interventional trial	4 weeks or 5 half-lives (whichever is longer)
Unstable dose of NSAIDs (including selective COX-2 inhibitors)	2 weeks
Analgesics other than NSAIDs, paracetamol/acetaminophen, and low strength opioids PRN	2 weeks
Systemic corticosteroids > 10 mg prednisone equivalent	2 weeks
Unstable dose of systemic corticosteroids ≤ 10 mg prednisone equivalent	2 weeks
Intra-articular corticosteroids injections	4 weeks
Intramuscular or intravenous corticosteroid treatment	4 weeks
Live vaccinations	6 weeks
Oral or topical retinoids	4 weeks
Photochemotherapy (e.g. PUVA)	4 weeks
Phototherapy (UVA or UVB)	2 weeks
Topical skin treatments (except in face, eyes, scalp and genital area during screening, only corticosteroids with mild to moderate potency)	2 weeks

5.5.9 Discontinuation of study treatment

Study treatment must be discontinued if the investigator determines that continuation of study treatment would result in a significant safety risk for a subject. The following circumstances **require** study treatment discontinuation:

- Withdrawal of informed consent
- Emergence of the following adverse events:
 - a. Any severe or serious adverse event that is not compatible with administration of study medication, including adverse events that require treatment with an unacceptable co-medication
 - b. Onset of lymphoproliferative disease or any malignancy except for treated basal cell carcinoma, treated actinic keratoses, treated in situ carcinoma of the cervix or non-invasive malignant colon polyps which are being or have been removed
 - c. Life-threatening infection
- Any laboratory abnormalities that in the judgment of the investigator are clinically significant and are deemed to place the subject at a safety risk for continuation in the study (A general guidance on clinically notable laboratory values is provided in ([Appendix 1](#))).
- Pregnancy
- Use of any biologic immunomodulating agent except secukinumab (please refer to [section 5.5.8](#) for the other prohibited medications). Any protocol deviation that results in a significant risk to the subject's safety

In addition to these requirements for study treatment discontinuation, the investigator should discontinue study treatment for a given subject if there is a lack of improvement or worsening of their symptoms, or if on balance, he/she thinks that continuation would be detrimental to the subject's well-being.

For any subject whose treatment code has been broken inadvertently for any reason, the appropriate personnel from the site and Novartis will assess whether study treatment should be discontinued.

The investigator must also contact the IRT to register the subject's discontinuation from study treatment.

Patients may voluntarily withdraw from the study for any reason at any time. They may be considered withdrawn if they state an intention to withdraw, fail to return for visits, or become lost to follow-up for any other reason.

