A proof-of-concept study conducted in patients with PsA (CAIN457A2206) suggesting a clinically meaningful response for signs and symptoms up to Week 16. The efficacy of secukinumab in PsA patients is further supported by positive results for signs and symptoms (i.e. ACR20/50, PASI75/90), resolution of dactylitis, enthesitis and inhibition of radiologic damage at Week 24 obtained in a phase III study (CAIN457F2306; N=606) employing an intravenous (i.v.) loading regimen (3x10 mg/kg) of secukinumab Q2W followed by secukinumab s.c. 75 mg or 150 mg administered Q4W. In another phase III study (CAIN457F2312; N=397) secukinumab also demonstrated positive efficacy results superior to placebo in patients with PsA through most components of the arthritic and skin measures of signs and symptoms and physical function in a population comprised of 65% naïve to TNF- α inhibitors and 35% patients who were inadequate responders to a TNF- α inhibitor. Based on the results of these phase 3 trials, secukinumab received FDA approval in January 2016 for the treatment of active PsA and AS in adult patients. Therefore, treatment with secukinumab may result in improvement of symptoms and functional joint manifestations in afflicted patients.

The completed studies of secukinumab recruited both biologic exposed or naïve PsA patients with or without psoriatic skin lesions at baseline. Therefore a need for predefined prospective data exist for these different subgroups of patients which the precise effects of targeting IL-17A can be observed more clearly. The present study will evaluate the safety and efficacy of treatment with two doses of secukinumab compared with placebo in patients with active psoriatic arthritis and concomitant psoriasis who are naïve to biologic medications including tumor necrosis factor alpha (TNF α), IL-6 and IL-12/23 inhibitors. Also in the blinded long term extension period of this study, the effect of increasing the dose in non-responders after each evaluation every 12 weeks visit will provide valuable information regarding the correlation between the level of disease activity and IL-17A inhibition.

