1.2 Purpose

The purpose of this study is to provide 16 week safety, efficacy and tolerability data in biologic naïve PsA patients with concomitant psoriatic skin lesions and evaluate the effect of secukinumab on PsA specific clinical findings such as dactylitis, enthesitis and psoriatic lesions. The study will also evaluate the early efficacy of the treatment at the first scheduled clinical visit after starting a treatment (i.e., at week 4) and investigate the remission status of all patients at each time points by evaluating the MDA, PASDAS and DAS28-CRP. This will be done in the blinded long term extension by increasing the dose to 300 mg in nonresponding

patients in 150 mg groups to confirm or support the role of higher IL-17A activity in PsA by evaluating the clinical response at every 12 weeks.

2 Study objectives

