 - Patients who did not meet the responder criteria at Week 16, 28 or 40 will start receiving secukinumab 300 mg s.c. every 4 weeks and will continue this dose up to Week 48.
- Patients on placebo (**Group 3**) regardless of their responder status will start receiving secukinumab 300 mg s.c. every 4 weeks from Week 16 up to Week 48.

Rescue medication will not be allowed during the day of the clinical visit and before completion of Week 16 assessments ([Section 5.5.6](#)). Although no subject will be restricted from receiving necessary rescue medications for lack of benefit or worsening of disease, patients will be discontinued from the study if rescued with prohibited biologics (as described in [Section 5.5.8](#)) and should obtain end of study assessments at the earliest possible date, provided consent to do so has not been withdrawn.

Figure 3-1 Study design

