5.2 Treatment groups

At the Baseline Visit, patients will be assigned via Interactive Response Technology (IRT) in a 2:2:1 ratio to one of the three treatment groups (secukinumab 300 mg s.c., secukinumab 150 mg s.c. or placebo s.c.).

Treatment Period 1

- **Group 1- Secukinumab 300 mg:** secukinumab 300 mg (two s.c. injections of the 150 mg dose) once weekly for five weeks (at Baseline, Weeks 1, 2, 3, and 4), followed by dosing every four weeks.
- **Group 2- Secukinumab 150 mg:** secukinumab 150 mg (one s.c. injection of the 150 mg dose and one s.c. injection of placebo) once weekly for five weeks (at Baseline, Weeks 1, 2, 3, and 4), followed by dosing every four weeks.
- **Group 3- Placebo:** placebo (two s.c. injection of 150 mg secukinumab placebo per dose) once per week for five weeks (at Baseline, Weeks 1, 2, 3, and 4), followed by dosing every four weeks.

Treatment Period 2

- Patients receiving secukinumab 300 mg (**Group 1**) will continue to receive the same dose up to Week 48.
- At Weeks 16, 28 and 40 patients on secukinumab 150 mg (**Group 2**) will be classified as responders ($\geq 20\%$ improvement from BL in both tender and swollen joint counts) or non-responders.
 - At Weeks 16, 28 and 40 patients on secukinumab 150 mg (Group 2) who are responders will continue to receive secukinumab 150 mg (1.0 mL) plus placebo (1.0 mL) every 4 weeks until next evaluation of responder status at Weeks 28 or 40.
 - Patients who did not meet the responder criteria at Week 16, 28 or 40 will start receiving secukinumab 300 mg s.c. every 4 weeks and will continue this dose up to Week 48.
- Patients on placebo (**Group 3**) regardless of their responder status will start receiving secukinumab 300 mg s.c. every 4 weeks from Week 16 up to Week 48.

Patients will self-administer all secukinumab and placebo doses at the study site up to Week 48. After they have received training by the site on how to self-administer their secukinumab and placebo doses.

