5.4 Treatment blinding

Patients, investigators/site staff, persons performing assessments, and Novartis study personnel will remain blinded to individual treatment assignment from the time of randomization until the final database lock using the following methods:

1. Randomization data will be kept strictly confidential until the time of unblinding, and will not be accessible by anyone else involved in the study with the following exceptions:
 - Specific vendors whose role in trial conduct requires their unblinding (e.g., IRT)
 - Drug Supply Management (DSM);
2. The identity of secukinumab and placebo prefilled syringes (PFS) will be concealed by identical packaging, labeling, schedule of administration, and appearance.

As the primary analysis time point is Week 16, there will be a database lock after all patients have completed the Week 16 visit and data are clean and complete. At that time, only the statistician and programmer(s) from the designated CRO will be unblinded in order to perform the analysis. Results from the analyses of all data through Week 16, will be reported. For publication purposes, summary results from the Week 16 primary analysis time point may be shared with the health care community, however individual subject-level data will remain blinded until the end of the trial.

Unblinding will only occur in the case of subject emergencies (see [Section 5.5.12](#)), at the time of the primary analysis (Week 16) for designated CRO personnel only, and at the conclusion of the study.

A full analysis of all data will be performed when all patients have completed the study.

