⁴ These assessments are source documented only and will not be entered into the eCRF
⁵ Not necessary if done within past 3 months. If not, should be scheduled only after patient has met inclusion/exclusion criteria
⁶ Fasting sample
⁷ Tests performed locally using kits supplied by central lab
⁹ Those patients on secukinumab 150 mg who are non-responders at Week 16, 28, or 40 will start receiving secukinumab 300 mg s.c. every 4 weeks up to Week 48.

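### The SAP's Up-titrated Subset is limited to completers, so a response rate on it omits patients who stopped after moving to 300 mg; separately, protocol 5.5.9 should say that non-response at a switch visit is not in itself a reason to stop

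*Protocol*

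**What the plan says.** **The subset.** SAP 2.2 builds the Up-titrated Subset from patients who completed and whose dose was raised from 150 mg to 300 mg in Treatment Period 2 because of their response status. SAP 2.2.1 makes every subset in 2.2 a planned subgroup of interest. Protocol 5.5.13 treats participation as complete once the Week 52 visit is done. Protocol section 6 brings patients who stop treatment early to a final visit about four weeks after their last dose.

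**The dose increase.** Group 2 patients are classed as responders if both joint counts have improved by at least 20% from baseline. For the others, protocol 5.2 says: "Patients who did not meet the responder criteria at Week 16, 28 or 40 will start receiving secukinumab 300 mg s.c. every 4 weeks". Section 3.1 and footnote 9 to Table 6-1 say the same. Placebo patients, "regardless of their responder status will start receiving secukinumab 300 mg s.c. every 4 weeks from Week 16 up to Week 48". Protocol 1.1 gives the reason for the up-titration: "the effect of increasing the dose in non-responders after each evaluation every 12 weeks visit will provide valuable information". Section 1.2 repeats that aim. It is not among the objectives in section 2.

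**The stopping clause.** After a list of circumstances that require discontinuation, protocol 5.5.9 adds that "the investigator should discontinue study treatment for a given subject if there is a lack of improvement or worsening of their symptoms". The same sentence also covers a patient for whom the investigator judges continuation harmful overall. It names no visit or threshold and does not refer to the up-titration. Under 5.4, site staff "will remain blinded to individual treatment assignment from the time of randomization until the final database lock".

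**Other summaries of the same patients.** SAP 2.4.1 lists a 150 mg to 300 mg (NR) group for efficacy over the entire treatment period. SAP 2.1 places efficacy after Week 16 on the Full Analysis Set. SAP 2.5.2 and 2.7.2 add versions of the binary summaries with non-responder imputation to Week 52.

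**The concern.** Completion is decided after the switch. Limiting the subset to completers therefore selects on something that the higher dose, or its failure, may have influenced. Patients who stop for want of effect or for an adverse event are the ones left out. A response rate on this subset would describe those who stayed, while a reader would naturally take it as the result of raising the dose in non-responders.

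A smaller matter lies upstream. A blinded investigator with an unimproved patient at Week 16, 28 or 40 does not know whether a dose increase is due, and 5.5.9 read alone points toward stopping. Any Group 2 non-responder stopped at that visit contributes nothing to the up-titration question. What is at stake in both cases is how Treatment Period 2 data, which are mainly descriptive, are read.

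**Working it through.** **Plan figures.** The documents give no size, response rate or attrition rate for the up-titrated group, so there is no figure on this point to reproduce. The only attrition figure is 10% loss to follow-up (protocol 4 and 9.7), which is a different quantity. The sample size of 88 and 44 in protocol 9.7 does reproduce with the stated inputs, but it concerns 300 mg versus placebo at Week 16 and is not affected.

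**Step 1: who is left out.**

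| Group 2 non-responder | Subset as defined | Subset as proposed below |
|---|---|---|
| Stopped at the switch visit, never given 300 mg | out | out |
| Given 300 mg, then stopped for any reason | out | in |
| Given 300 mg and completed | in | in |

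Only the second row changes. A patient stopped instead of being up-titrated is outside the subset under either definition.

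**Step 2: size of the completer effect.** Let c be the response rate among completers and d the share of up-titrated patients who do not complete.

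- Rate in the subset as defined: c
- Rate with discontinuers counted as non-responders: c(1 − d)
- Gap: c − c(1 − d) = c × d
- Ratio: 1/(1 − d)

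Both c and d are assumed:

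| d | c = 30%: rate, gap | c = 50%: rate, gap | Ratio |
|---|---|---|---|
| 0% | 30.0%, 0 | 50.0%, 0 | 1.00 |
| 5% | 28.5%, 1.5 points | 47.5%, 2.5 points | 1.05 |
| 10% | 27.0%, 3.0 points | 45.0%, 5.0 points | 1.11 |
| 20% | 24.0%, 6.0 points | 40.0%, 10.0 points | 1.25 |

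In whole patients (also assumed): 40 up-titrated, 8 stopped, 19 responders. Completers give 19/32 = 59.4%; all up-titrated give 19/40 = 47.5%.

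**Step 3: how many could be up-titrated at one visit.** ACR20 requires 20% improvement in both joint counts plus three of five other domains (protocol 6.4.1). Every ACR20 responder therefore passes the joint-count rule, and the share failing it is at most 1 − ACR20 rate. Protocol 3.3 gives Week 24 ACR20 rates of 50.0% and 51.0% for 150 mg in two earlier trials. If those rates held here, at most 100 × (1 − 0.500) = 50 or 100 × (1 − 0.510) = 49 of 100 Group 2 patients would be non-responders at a given visit. This is a ceiling on those eligible for the switch, not a count of patients stopped. The number stopped under 5.5.9 cannot be estimated from the documents.

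**Step 4: the two protocol rules side by side.** The up-titration has named visits and a numeric criterion. The 5.5.9 sentence has neither and is set apart from the circumstances that require stopping. A patient can also fail the joint-count rule and still have improved in other respects, so the two rules overlap only in part.

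**The case against.** The strongest reply is that little depends on this subset. The 150 mg to 300 mg (NR) group on the Full Analysis Set, with non-responder imputation, keeps patients who stop after the switch and counts them as non-responders on the binary endpoints. No visible SAP section assigns an endpoint to the Up-titrated Subset, whereas 2.7.2 does so for the Dactylitis and Psoriasis Subsets. SAP 2.13 is not in the text available, so its use there cannot be checked. All of this stands and limits the point to analyses run on the subset. It does not justify the definition.

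It is also fair to say that the gaps above are algebra on assumed inputs, and that the earlier trials differ from this one. One of them included 35% inadequate responders to a TNF inhibitor (protocol 1.1), while this trial enrols biologic-naïve patients and first applies the rule at Week 16. That stands too.

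On 5.5.9, a reader might infer that sites hold two flatly opposing orders. The documents do not support that. The sentence is a clinical-judgement clause, and the switch schedule is the more specific rule. Section 3.1 allows rescue for patients without benefit and requires exit only after a prohibited biologic. Section 5.5.6 defines rescue to include patients with no benefit and bars it until the Week 16 assessments are complete. Both sections expect some non-improvers to remain. Nor is the placebo switch in doubt, since it does not depend on response. What remains is that 5.5.9 does not mention the up-titration visits.

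**Conclusion.** The point holds and is minor. As SAP 2.2 stands, a response rate on the Up-titrated Subset is a completers-only rate, above the non-responder-imputed rate by c × d. That is 1.5 to 10 points over the assumed ranges (c of 30% or 50%, d of 5% to 20%) and zero if every up-titrated patient completes.

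Three stronger conclusions might be drawn, and none is supported:

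- **That the primary result is at risk.** The ACR20 test at Week 16 precedes the switch and does not use this subset.
- **That all up-titration results are limited to completers.** The Full Analysis Set summaries with non-responder imputation are not.
- **That 5.5.9 produces the subset problem.** Patients stopped instead of being up-titrated never enter the subset. The completion condition removes those who stop after the switch, for any reason.

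The silence in 5.5.9 is a separate and lesser matter. It may reduce the number who reach the dose increase, by an unknown amount and with no demonstrated direction of effect on the results.

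**What to change.** **SAP 2.2.** Define the Up-titrated Subset as all Group 2 patients who received 300 mg after meeting the non-responder rule. Count discontinuers as non-responders for binary endpoints, and give the completers' result as a sensitivity analysis.

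**Protocol 5.5.9.** Add one sentence: failing the responder criteria at Week 16, 28 or 40 is not in itself a reason to stop study treatment. Leave stops for worsening, safety, detriment and patient choice as they are, and do not restrict investigator judgement before Week 16.

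**Reporting.** Show how many Group 2 patients stopped for lack of improvement before and after up-titration. Reasons for discontinuation are already planned in SAP 2.3.1, so the disposition form needs changing only if this reason is not recorded separately.

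**Cost.** One changed definition, one amended sentence with a site letter, and one disposition line; no extra visits or patients. The reported rate after up-titration may be lower, and investigators have slightly less latitude to stop for non-response alone at the switch visits. The SAP's revision history places the subset definition after the Week 16 lock, so from then on the protocol sentence could help only at remaining Week 28 or 40 visits. The SAP change does not depend on that.
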